**Sample Size Justification:**

Enrollment of 20 subjects with schizophrenia is estimated to provide >80% power to detect a median effect size of Cohen's *d*=0.5. Discontinued or withdrawn subjects and subjects for whom MMN is not available for all three study periods may be replaced. The sample size chosen of 20 completed subjects is expected to be sufficient to explore the changes in MMN between CVN058 and placebo as well as safety and tolerability of CVN058 in this population.

### 3.0 LIST OF ABBREVIATIONS

5-HT	5-hydroxytryptamine (serotonin)
5-HT 3	5-hydroxytryptamine (serotonin) receptor 3
AE	adverse event
ALT	alanine aminotransferase
ANCOVA	analysis of covariance
AST	aspartate aminotransferase
AUC	area under the plasma concentration-time curve
AUC t	area under the plasma concentration-time curve from 0 to time of last quantifiable concentration
BA	bioavailability
BMI	body mass index
CIAS	cognitive impairment associated with schizophrenia
CL/F	apparent clearance after extravascular administration
C max	maximum observed plasma concentration
CNS	central nervous system
CRO	contract research organization
CS	clinically significant
CSF	cerebrospinal fluid
C-SSRS	Columbia-Suicide Severity Rating Scale
DSM -V	Diagnostic & Statistical Manual of Mental Disorders, 5 th Edition – Text Revision
eCRF	electronic case report form
DNA	deoxyribonucleic acid
ECG	electrocardiogram
EEG	electroencephalography
EMA	European Medicines Agency
ERP	evoked response potential
FDA	Food and Drug Administration
FM	frequency-modulation
FSH	follicle-stimulating hormone
FSI	fast-spiking interneurons
F z	frontal electrodes
F z ,C z	frontocentral electrodes
GABA	γ-aminobutyric acid
GCP	Good Clinical Practice
GGT	γ-glutamyl transferase
HBsAg	hepatitis B surface antigen
hCG	human chorionic gonadotropin
HCV	hepatitis C virus
HIV	human immunodeficiency virus
ICH	International Conference on Harmonisation
IEC	independent ethics committee
INR	international normalized ratio
IRB	institutional review board
IUD	intrauterine device

---

K 2 EDTA	potassium ethylenediamine tetraacetic acid
LFT	liver function test
MedDRA	Medical Dictionary for Regulatory Activities
MMN	mismatch negativity
NCS	not clinically significant
NMDAR	N-methyl-D-aspartate receptor
NFSI	non-fasting spiking interneurons
OTC	Over-the-counter
PANSS	Positive and Negative Syndrome Scale
PD	pharmacodynamic(s)
PI	principal investigator
PK	pharmacokinetic(s)
PT	prothrombin time
PTT	partial thromboplastin time
PTE	pretreatment event
PV	parvalbumin
P z	parietal electrodes
P50 Ratio	ratio of S2 to S1
RNA	ribonucleic acid
QTcB	QT interval with Bazett correction method
QTcF	QT interval with Fridericia correction method
SAE	serious adverse event
SAP	statistical analysis plan
SSR	steady state response
SUSAR	suspected unexpected serious adverse reaction
t 1/2z	terminal elimination half-life
CVN058	also known as ENV8058 and TAK-058
TEAE	treatment-emergent adverse event
t max	time to reach C max
ULN	upper limit of normal
V z/F	apparent volume of distribution during the terminal phase
WHODRUG	World Health Organization Drug Dictionary

## 4.0 INTRODUCTION

### 4.1 Background

Schizophrenia is a complex disorder comprising several clinical features that are highly variable among affected individuals. Probably the most well-known schizophrenia symptom domains are the so-called positive symptoms, e.g., hallucinations, delusions, disorganization of thought, bizarre behavior, and incongruity of affect. Negative symptoms include avolition (loss of motivation), blunt affect, alogia (reduced speech), and anhedonia (reduced ability to experience pleasure). Cognitive impairment associated with schizophrenia (CIAS) usually precedes psychosis and is observed in most cases involving deficits in a broad range of domains. Finally, patients with schizophrenia often experience depression and anxiety, express hostility, and become demoralized ([Thaker, 2001](#)).

Cognitive impairment is considered a core feature of schizophrenia and represents an area of significant unmet medical need. Cognitive deficits in schizophrenia include problems in speed of processing, attention/vigilance, working memory, verbal learning, visual learning, reasoning and problem solving, and social cognition ([Green, 2006](#)). These cognitive deficits are believed to underlie much of the significant functional impairments observed in schizophrenia, such as impairment in independent living skills, social functions, vocational functioning, and self-care ([Harvey, 2007](#)). Thus, the core nature of CIAS and the associations that have been demonstrated with functional disability suggest that improving cognitive impairment may lead to improved functional outcomes ([Heinrichs, 2005](#)).

The understanding of CIAS has evolved significantly in recent years and led to new therapeutic strategies. In postmortem samples from schizophrenic patients, studies consistently reveal reduced levels of enzymes that synthesize the inhibitory neurotransmitter  $\gamma$ -aminobutyric acid (GABA) in the prefrontal cortex ([McNally, 2013](#)) a key center for higher cognitive function. The GABAergic neurons deficient in the cortex are termed fast-spiking interneurons (FSIs), and they express the marker parvalbumin (PV) ([McNally, 2013](#)). These PV+ FSIs are chemically coupled and release GABA in a rhythmic pattern that synchronizes the activity of local cortical pyramidal neurons ([Cardin, 2009](#)). This synchronization, which is essential for cognition, is disrupted in patients [[\(McNally, 2013\)](#), [\(Cardin, 2009\)](#)] [[\(Whittington, 1997\)](#), [\(Rotaru, 2012\)](#), [\(Gonzalez-Burgos, 2012\)](#)]. These and other human and animal model data implicate FSI hypofunction, and a resulting imbalance in the excitation/inhibition balance in cortical regions, in CIAS.

Based on this emerging insight into disease pathophysiology, a therapeutic that restores the normal function of the cortical pyramidal neuron/FSI microcircuit would be expected to improve cognitive function in patients with schizophrenia. One strategy for boosting the function of this circuit is to inhibit a second population of inhibitory GABAergic interneurons, known as non-fast spiking interneurons (NFSIs), which project locally onto the FSIs and the dendrites of the pyramidal neurons. These NFSIs are modulated by a wide variety of inputs, particularly excitatory glutamatergic efferents from the thalamus, and noradrenergic, cholinergic, and serotonergic efferents from subcortical regions [[\(Tian, 2010\)](#), [\(Kawaguchi, 1998\)](#), [\(Kawaguchi, 1997\)](#), [\(Lee, 2010\)](#)]. Thus, NFSIs appear to integrate state-dependent information and release GABA to regulate pyramidal neuron/FSI microcircuits.

Mismatch negativity (MMN) is an established biomarker of cortical function (Javitt, 2015). This signal is obtained as an evoked potential during an auditory oddball task, in which a subject is repeatedly exposed to auditory tones and a small proportion of those tones (the “deviant” stimuli) differ from the others (the “standard” stimuli) in their frequency or duration. Typically, the tones are presented and the evoked potentials are recorded while subjects are engaged on a different task, such as reading. Normally, the occurrence of a deviant stimulus increases the amplitude of the negative component in the evoked potential occurring at around 200 msec. MMN is the difference in amplitude between deviant and standard stimuli responses, and is considered to represent an aspect of preattentive novelty detection. MMN is consistently reduced in schizophrenia patients relative to healthy individuals, a finding extensively replicated and with a large effect size (Cohen’s  $d = 1$ ). MMN reduction in schizophrenia has been shown to reflect impaired N-methyl-D-aspartate receptor (NMDAR) function at the level of supratemporal auditory cortex, dependent on cortical interneuron modulation of pyramidal cell activity and NMDA receptor-dependent (Lee, 2017).

#### 4.2 Non-Clinical

CVN058 (also known as ENV8058 or TAK-058) is a small molecule that potently and selectively antagonizes the 5-hydroxytryptamine (5-HT) receptor type 3 (5-HT3). 5-HT3 is a cyst-loop family ligand-gated ion channel that allows cations to pass into the neurons when activated by serotonin, and is highly expressed in NFSIs [(Lee, 2010), (Lummis, 2012)]. The receptor is a pentamer consisting of at least two 5-HT3a subunits and 3 other subunits; in the central nervous system (CNS) the receptor is almost exclusively a homomeric pentamer comprised of 5-HT3a (Kawaguchi, 1997). The 5-HT3 channel opens when serotonin molecules interact with the 2 ligand recognition sites in the extracellular side of the receptor. Influxed calcium and other positive ions depolarize the NFSIs, leading to GABA release. CVN058 is orally absorbed and readily passes the blood brain barrier, allowing it to occupy cortical 5-HT3 receptors (50% occupancy of rat cortical 5-HT3 receptors is achieved at plasma concentrations of approximately 5.8 ng/mL). CNS 5-HT3 receptor occupancy is correlated with efficacy in a rat model of cognition where it reverses deficits in novel object recognition induced by subchronic phencyclidine treatment. Thus, CVN058 is a novel therapeutic candidate that may improve cognitive function by inhibiting specific subsets of cortical interneurons.

Additional information from the nonclinical studies can be found in the current Investigator’s Brochure.

#### 4.3 Clinical

Two human clinical studies of CVN058 have been completed (ENV8058\_101 and TAK-058-1002).

CVN058 was well tolerated up to a dose of 150 mg administered orally as a single dose in aqueous solution (Study ENV8058\_101). There were no deaths or other serious adverse events (SAEs) reported in this study and no subject discontinued study due to a treatment-emergent adverse event (TEAE). There were no clinically significant (CS) laboratory abnormalities, electrocardiogram (ECG) changes or changes in vital signs in the completed single dose study.

The mean  $C_{max}$  and area under the plasma concentration–time curve (AUC) values of CVN058 increased less than proportionally with increasing CVN058 dose across the dose range of 5 to 150 mg, but mean  $C_{max}$  and AUC values increase in an approximately dose proportional manner across the 5 to 45 mg dose range. The rate of appearance of CVN058 in plasma was rapid with median time to  $C_{max}$  ( $t_{max}$ ) values of 1 to 1.25 hours across the dose range of 5 to 150 mg. The mean terminal elimination half-life ( $t_{1/2z}$ ) values of CVN058 ranged from approximately 2.8 to 10.5 hours across the cohorts; the lower doses (5 to 30 mg) had lower mean  $t_{1/2z}$  values compared to the higher doses (45 to 150 mg). There were no trends with mean apparent clearance (CL/F) values of CVN058 with increasing dose from 5 to 45 mg, but faster apparent clearance was observed at the 75 and 150 mg doses, possibly due to decreased bioavailability (BA) at higher doses. The mean apparent volume of distribution ( $V_z/F$ ) increased as dose increased. Excretion of unchanged CVN058 in the urine was  $\leq 2.3\%$  of the administered CVN058 dose over the dose range evaluated.

In the multiple-rising dose study (TAK-058-1002), CVN058 was well-tolerated at daily doses of 25, 75, and 150 mg for 7 days, and at a single 300 mg dose, in aqueous solution. There were no deaths or other SAEs reported in this study and no subject discontinued study due to a TEAE. There were no clinically significant laboratory abnormalities, ECG changes or changes in vital signs in the completed single dose study. Following single or multiple doses, the mean  $C_{max}$  and AUC values of CVN058 increased less than proportionally with increasing CVN058 dose across the dose range of 25 to 300 mg. No accumulation was observed following daily administration. CVN058 concentrations in cerebrospinal fluid (CSF) were assessed after daily doses of CVN058 75 mg for 5 days. The CSF concentrations averaged 17.5 ng/mL, or approximately 1% of the concentration in plasma.

#### 4.4 Rationale for the Proposed Study

This study will explore central target engagement and proof of mechanism by measuring auditory evoked potential MMN as a pharmacodynamic (PD) marker of CNS response to the selective 5-HT3 receptor antagonist CVN058. It has been reported that subjects with schizophrenia commonly demonstrate a deficit in neural processing that is manifested as a reduction in MMN and impairment of auditory sensory gating (P50) (Javitt and Sweet, 2015). Other 5-HT3 receptor antagonists have been reported to improve impairments in auditory evoked potentials in schizophrenic subjects. In a study with ondansetron, a 5-HT3 receptor antagonist, using P50 auditory gating as the auditory evoked potential measure, subjects were given a single dose of ondansetron (16 mg) or placebo in a double-blind, placebo-controlled, randomized and balanced crossover design ([Adler, 2005](#)). Serial measurements of the P50 evoked potential were done at Baseline and 1, 2, and 3 hours after receipt of placebo or ondansetron. The results of the study indicated that ondansetron significantly enhanced P50 auditory gating in subjects with schizophrenia. Tropisetron, a 5-HT3 antagonist that also has  $\alpha 7$  nicotinic cholinergic agonist activity, has similarly been shown to improve P50 auditory gating in subjects with schizophrenia ([Koike, 2005](#)).

While the P50 signal is likely a reflection of brainstem and thalamic network activity and is sensitive to antipsychotic treatment, MMN is thought to reflect excitation-inhibition balance in cortical circuits and is not sensitive to antipsychotic treatment (Javitt and Sweet, 2015). Therefore, to evaluate the potential for CVN058 to improve cognitive function in schizophrenics,

CONFIDENTIAL

MMN will be used as a PD marker. The study will be performed as a 3-way crossover to assess the effect on MMN of CVN058 at two dose levels relative to placebo, with each subject serving as his or her own control to reduce variability. P50 auditory gating will also be measured, as an exploratory endpoint, along with other potentially informative electrophysiological and psychometric parameters.

Medications that might inhibit or mask the effects of CVN058 will not be permitted as concomitant medications. These include serotonin reuptake inhibitors which increase synaptic serotonin levels, as well as drugs that bind to 5-HT3 at clinically relevant concentrations or are reported to inhibit signaling through 5-HT3 non-competitively, including some antipsychotic drugs [([Eisensamer](#), 2005), ([Eisensamer](#), 2003), ([Rammes](#), 2004)]. Permissible antipsychotic medications are risperidone (Risperdal), haloperidol (Haldol), quetiapine (Seroquel), aripiprazole (Abilify) and paliperidone (Invega).

## 5.0 STUDY OBJECTIVES AND ENDPOINTS

### 5.1 Objectives

#### 5.1.1 Primary Objective

- To determine whether improvement in MMN is demonstrated after administration of CVN058 compared to placebo in subjects with schizophrenia.

#### 5.1.2 Secondary Objective

- To assess the safety and tolerability of single doses of CVN058 in subjects with schizophrenia.

#### 5.1.3 Exploratory Objectives

- To determine whether improvement in P50 auditory gating, gamma power, and P300 is demonstrated after administration of CVN058 compared to placebo in subjects with schizophrenia.
- To assess the pharmacokinetics (PK) of CVN058 following a single dose to subjects with schizophrenia.
- To explore the exposure-response relationship for CVN058 in subjects with schizophrenia.

### 5.2 Endpoints

#### 5.2.1 Primary Endpoints

- Mean amplitude of duration MMN at 5 electrodes surrounding frontal (Fz) electrodes following administration of CVN058 compared to placebo.

#### 5.2.2 Secondary Endpoint

- Percentage of subjects who experience at least 1 TEAE
- Percentage of subjects who experience at least 1 clinically significant abnormal laboratory test result

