- (h) Clinical laboratory tests (hematology, serum chemistry, and urinalysis) will be collected at Screening and prior to check-out at End of Treatment or Early Termination, and at the Investigator discretion if a Follow-up Visit is indicated.
- (i) Audiometric Screening assessment conducted according to local practice.
- (j) A FSH level will be obtained on post menopausal women (defined as continuous amenorrhea of at least 2 years and not surgically sterile).
- (k) For the EEG battery, testing will be done at Day 1 starting approximately 1.5 hours post dose for each period and will last approximately 2 hours. NOTE: Subjects should refrain from drinking coffee and smoking approximately 1 hour prior to the EEG assessment until discharge from clinic at the end of the afternoon.
- (l) MMN will be the first EEG assessment conducted in the battery.
- (m) One blood sample (6 mL) will be collected for pharmacogenomic analysis prior to study drug administration on Day 1 of Period 1 only. If isolation of DNA from the first sample was not successful or possible, a second aliquot of blood may be taken, if feasible.
- (n) Two 2.5 mL whole blood samples will be collected for each Period (Periods 1, 2, and 3) on Day 1 at pre-dose, and 4 hours post- dose
- (o) Blood samples (6 mL) for PK analyses will be collected at pre -dose (within 15 minutes prior to dosing), and 1 and 4 hours post dose.
- (p) Dosing will only occur on Day 1 of each period, and signals the start of the post-dose Day 1 visit assessments.
- (q) PTEs will be collected from signing of informed consent up until dosing on Day 1.
- (r) Any adverse event with onset or exacerbation after dosing on Day 1 of Period 1 will be captured as an AE or SAE.
- (s) The Screening/Baseline C-SSRS will be administered at Screening and the Since Last Visit C-SSRS will be administered after EEG/ERP collection on each dosing day, and End of Treatment or Early Termination (if applicable).
- (t) The Screening/Baseline PANSS will be collected at Screening, approximately 4 hours after each dose (post EEG) and at Early Termination (if applicable).

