### **8.3.3 Final Visit/End of Treatment**

The Final Visit additional assessments will occur prior to Discharge from the clinic at the end of Treatment Period 3, Day 1, as outlined in [Appendix A](#).

For all subjects who received any study medication, the investigator must complete the End of Study eCRF page.

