**Table 9.c Approximate Blood Volume**

Sample Type	Sample Volume (mL)	Screening (x1)	Number of Samples per Period (x 3 Periods)	End of Treatment	Total Volume (mL)
Safety Laboratory Samples (a)	12.5	1	--	1	25
Hepatitis Panel	5	1	--		5
FSH (b)	3	1	--		3
PK Samples	6	--	9	--	54
DNA Sample	6	--	1 (c)	--	6
RNA Samples	5	--	6	--	30
Total Blood Sampling Volume (per Study)					123

(a) Includes Hematology, serum chemistry, and coagulation panel.

(b) FSH level will be obtained for female subjects at Screening if they are postmenopausal (i.e. last regular menstrual cycle >2 years) and not surgically sterile.

(c) Only collected in Day 1, Period 1.

The maximum volume of blood at any single day is approximately 40 mL, and the approximate total volume of blood for the study is approximately 123 mL.

Direct venipuncture is the preferred method of blood collection. Any other method will need to be approved by the Sponsor.

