#### **12.1.5 Safety Analysis**

The Safety Set will be used for all summaries of TEAEs, laboratory tests, and vital signs. All safety data will be summarized by treatment.

AEs will be presented in listings. TEAEs will be classified according to system organ class and preferred term and will be tabulated with a breakdown by treatment and by event severity. Similar TEAE tabulations will be performed on those events assessed by the investigator as related to study drug.

Individual results of vital signs will be listed and observed values and changes from Baseline in vital signs will be summarized by treatment.

Physical exam findings, suicidality assessments (C-SSRS), and PANSS scores will be presented in data listings.

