- (h) Clinical laboratory tests (hematology, serum chemistry, and urinalysis) will be collected at Screening and prior to check-out at End of Treatment or Early Termination, and at the Investigator discretion if a Follow-up Visit is indicated.
- (i) Audiometric Screening assessment conducted according to local practice.
- (j) A FSH level will be obtained on post menopausal women (defined as continuous amenorrhea of at least 2 years and not surgically sterile).
- (k) For the EEG battery, testing will be done at Day 1 starting approximately 1.5 hours post dose for each period and will last approximately 3 hours. NOTE: Subjects should refrain from drinking coffee and smoking approximately 1 hour prior to the EEG assessment until discharge from clinic at the end of the afternoon.
- (l) MMN will be the first EEG assessment conducted in the battery.
- (m) One blood sample (6 mL) will be collected for pharmacogenomic analysis prior to study drug administration on Day 1 of Period 1 only. If isolation of DNA from the first sample was not successful or possible, a second aliquot of blood may be taken, if feasible.
- (n) Two 2.5 mL whole blood samples will be collected for each Period (Periods 1, 2, and 3) on Day 1 at pre-dose, and 5 hours post-dose.
- (o) Blood samples (6 mL) for PK analyses will be collected at pre -dose (within 15 minutes prior to dosing), and 1 and 5 hours post dose.
- (p) Dosing will only occur on Day 1 of each period, and signals the start of the post-dose Day 1 visit assessments.
- (q) PTEs will be collected from signing of informed consent up until dosing on Day 1.
- (r) Any adverse event with onset or exacerbation after dosing on Day 1 of Period 1 will be captured as an AE or SAE.
- (s) The Screening/Baseline C-SSRS will be administered at Screening and the Since Last Visit C-SSRS will be administered after EEG/ERP collection on each dosing day, and End of Treatment or Early Termination (if applicable).
- (t) The Screening/Baseline PANSS will be collected at Screening, approximately 5 hours after each dose (post EEG) and at Early Termination (if applicable).

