#### 7.5 Criteria for Discontinuation or Withdrawal of a Subject

The primary reason for discontinuation or withdrawal of the subject from the study or study medication should be recorded in the eCRF using the following categories. For screen failure subjects, refer to [Section 9.1.17](#).

1. Pretreatment event (PTE) or AE. The subject has experienced a PTE or AE that requires early termination because continued participation imposes an unacceptable risk to the subject's health or the subject is unwilling to continue because of the PTE or AE.
2. Liver Function Test (LFT) Abnormalities

Study medication should be discontinued immediately with appropriate clinical follow-up (including repeat laboratory tests, until a subject's laboratory profile has returned to normal/baseline status, see [Section 9.1.8](#)), if the following circumstances occur at any time during study medication treatment:

- ALT or AST  $>8 \times$ ULN, or
- ALT or AST  $>5 \times$ ULN and persists for more than 2 weeks, or
- ALT or AST  $>3 \times$ ULN in conjunction with elevated total bilirubin  $>2 \times$  ULN or international normalized ratio (INR)  $>1.5$ , or
- ALT or AST  $>3 \times$ ULN with appearance of fatigue, nausea, vomiting, right upper quadrant pain or tenderness, fever, rash and/or eosinophilia ( $>5\%$ ).

3. Significant protocol deviation. The discovery post randomization or after the first dose of study medication that the subject failed to meet protocol entry criteria or did not adhere to protocol requirements, and continued participation poses an unacceptable risk to the subject's health.
4. Lost to follow-up. The subject did not return to the clinic and attempts to contact the subject were unsuccessful. Attempts to contact the subject must be documented.

5. Voluntary withdrawal. The subject (or subject's legally acceptable representative) wishes to withdraw from the study. The reason for withdrawal, if provided, should be recorded in the eCRF.

Note: All attempts should be made to determine the underlying reason for the withdrawal and, where possible, the primary underlying reason should be recorded (i.e., withdrawal due to an AE).

6. Study termination. The sponsor, IRB, IEC, or regulatory agency terminates the study.

7. Pregnancy. The subject is found to be pregnant.

Note: If the subject is found to be pregnant, the subject must be withdrawn immediately. The procedure is described in [Section 9.1.10](#).

8. Other.

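### Laboratory data are to be summarised by treatment, but a completer's only scheduled post-dose sample follows all three regimens and cannot be attributed to any one of them

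*Protocol*

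**What the plan says.** The second secondary endpoint (5.2.2 in Versions 1.0 and 3.0, 4.2.2 in Version 2.0) is the "Percentage of subjects who experience at least 1 clinically significant abnormal laboratory test result". It names no treatment and no comparator.

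The schedule is in Appendix A, footnote (h), of Versions 1.0 and 2.0: "Clinical laboratory tests (hematology, serum chemistry, and urinalysis) will be collected at Screening and prior to check-out at End of Treatment or Early Termination", and further "at the Investigator discretion if a Follow-up Visit is indicated". The treatment-period columns carry no laboratory mark. End of Treatment is defined in Version 2.0, 8.3.3: "The Final Visit additional assessments will occur prior to Discharge from the clinic at the end of Treatment Period 3, Day 1".

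The reporting rule is in Version 2.0, 12.1.5 (Version 1.0, 13.1.5, has the same text): "The Safety Set will be used for all summaries of TEAEs, laboratory tests, and vital signs. All safety data will be summarized by treatment". No exception is made for laboratory tests.

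The liver-test criteria in 7.5 (Version 3.0, with the same text in Versions 1.0 and 2.0) require study medication to be stopped "if the following circumstances occur at any time during study medication treatment". One criterion depends on an elevation that lasts more than 2 weeks.

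**The concern.** In a three-period crossover, a by-treatment safety summary needs at least one observation that belongs to each period. Vital signs meet this: they are taken before the dose and twice after it in every period. Laboratory tests do not, and the blanket sentence overlooks the difference.

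A programmer who follows the sentence has one scheduled post-dose result per completer and three columns to put it in. The natural choice is the Period 3 regimen. An abnormality that arose after an earlier active dose would then appear under whatever came last, which in two sequences is placebo. That is a misleading display of a named secondary endpoint.

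The liver-test text raises a separate question. It reads as a check that operates between doses, but the schedule supplies no post-dose result until no dose remains.

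**Working it through.** **1. Confirm the number of scheduled draws.** Table 9.c (same figures in Versions 1.0 and 2.0) gives safety laboratory samples at 12.5 mL, one at Screening, none per period and one at End of Treatment. Rebuilding the total:

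12.5×2 + 5 (hepatitis panel) + 3 (FSH) + 6×9 (PK) + 6×1 (DNA) + 5×6 (RNA) = 25 + 5 + 3 + 54 + 6 + 30 = 123 mL.

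This reproduces the stated total of 123 mL.

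**2. Check that no per-period draw is hidden.** Daily volumes from the table's own entries, with PK 6×3 = 18 mL and RNA 5×2 = 10 mL per period:

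- Period 1: 18 + 10 + 6 = 34 mL
- Period 2: 18 + 10 = 28 mL
- Period 3 with the safety sample: 18 + 10 + 12.5 = 40.5 mL

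The stated maximum of about 40 mL is reached only on the Period 3 day. If a safety sample were drawn in every period, the total would be 123 − 25 + 12.5×4 = 148 mL and the Period 1 day 34 + 12.5 = 46.5 mL. Neither agrees with the table. So there is one scheduled post-dose draw per completer.

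**3. Coverage of dosing periods.** 20 completers × 3 periods = 60. A scheduled laboratory result falls within 20 of them (Period 3) and not within the other 40. With washouts of 7 to 10 days, the draw comes 7 to 10 days after the second dose and 14 to 20 days after the first.

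**4. Which regimen comes last.** From Table 6.a (A placebo, B 15 mg, C 150 mg):

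| Sequences | Order | Last regimen | Already taken |
|---|---|---|---|
| 1, 2 | ABC, BAC | C | A and B |
| 3, 4 | CAB, ACB | B | A and C |
| 5, 6 | BCA, CBA | A | B and C |

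Assume the 20 completers split 3 or 4 per sequence (4×3 + 2×4 = 20; the sections shown do not state the balance). Each regimen is then last in 3+3 = 6 to 4+4 = 8 subjects. Every completer has taken all three regimens by the time of the draw, so the columns of a by-treatment table would differ in order of exposure, not in what was received.

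**5. What splitting costs.** The chance of seeing at least one abnormal result is 1 − (1 − p)^n. The documents give no rate, so take p = 5% to 10% as an assumption:

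| n | p = 5% | p = 10% |
|---|---|---|
| 6 | 26% | 47% |
| 8 | 34% | 57% |
| 20 | 64% | 88% |

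**6. Liver-test text against the schedule.** Scheduled post-dose results before the last dose, for a completer: 0. Scheduled post-dose results in all: 1, which cannot by itself show an elevation lasting more than 2 weeks.

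**The case against.** The endpoint line does not ask for treatment groups, whereas the primary endpoint and nearly all the exploratory pharmacodynamic endpoints say they are compared with placebo. That stands. A reader might infer that the secondary endpoint cannot be computed; it can, as one percentage over all subjects.

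Attribution of results to regimens is ordinary SAP content, and the protocol nowhere assigns the final result to the last regimen. A reader might also infer that untested periods are counted as normal; no text says so. But the by-treatment sentence is itself in the protocol, names laboratory tests in the sentence before it, and no attribution rule can supply results that were not collected.

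It may be said that the last-regimen table is a fair Period 3 comparison, because earlier drug has gone: the longest mean half-life reported is about 10.5 hours, and 7 days is 168/10.5 = 16 half-lives. This answers carry-over of the drug, not of a laboratory abnormality, and the liver criteria themselves allow for elevations lasting beyond 2 weeks. Even if accepted, it would be a parallel comparison of 6 to 8 subjects per regimen.

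Early Termination draws do give some results after Period 1 or 2, but only in subjects who leave. Clinically significant abnormalities are also recorded as adverse events with a start date, but that date is when the finding was first noted, so one first seen at the last draw would still be dated to Period 3.

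On the liver text, it is tempting to call the rule inoperable. The documents do not support that: it applies at any time, one criterion is linked to symptoms, and unscheduled tests could trigger it.

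**Conclusion.** In Versions 1.0 and 2.0 the by-treatment rule does not fit the laboratory schedule. For a completer, one scheduled post-dose result follows all three regimens. A by-treatment table could only reflect the last regimen, in about 6 to 8 of 20 subjects each, mixed with earlier exposure, and one third of the sequences end on placebo after both active doses. The 6 to 8 assumes near-equal allocation to sequences. The mismatch itself does not depend on that assumption.

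The liver-test text and Appendix A are a smaller, separate mismatch: the text has no scheduled post-dose result to act on before the last dose.

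Version 3.0 is shown with the same endpoint and liver-test text, but its schedule and safety-analysis section are not shown, and Versions 4.0 and 5.0 are not shown at all. A reader might assume that the problem persists there. It may, but this has to be checked.

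**What to change.** In the safety-analysis section, exempt laboratory data from the by-treatment sentence. Report the secondary endpoint as the overall percentage of subjects with at least one clinically significant abnormal post-dose result, counting Early Termination and unscheduled results, and give the number of subjects with any post-dose result beside it. Add a shift table from Screening to end of study and a listing by sequence that shows the date of each result, with no treatment comparison. The shift table supplements the percentage and does not replace it.

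The sponsor should reconcile the liver-test text in 7.5 with Appendix A. Which of the two changes is a clinical decision, and no schedule or rule is proposed here.

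Before editing, check the corresponding sections of Versions 3.0 to 5.0.

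The statistical part costs a sentence and some table shells, with no extra blood and no extra visits. What is given up is a by-treatment laboratory comparison that the schedule cannot support.
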